7.3.1.4. Measure of impact (clinical malaria)

The vaccine impact will be estimated by the number of cases of clinical malaria averted over the relevant time frame per 1000 subjects vaccinated. The number of cases averted will be calculated as the difference of the estimated cases between the Control group and the vaccine group. Estimated cases in each group will be calculated as the area under the curve of the incidence of clinical malaria over time and expressed as cumulative cases averted per 1000 subjects followed-up during the relevant period. Results per site and overall will be summarized in tables.

7.3.1.5. Primary analysis of efficacy (primary objective)

A) Clinical malaria:

Analysis performed at Month 20:

Incremental efficacy of Fx012-14 versus (R012-20 + R012-14) over M2.5-M14 (first or only episode, PPS).

7.3.1.6. Secondary analyses of efficacy

A) Clinical malaria:

Analysis performed at Month 20:

- Incremental efficacy of Fx012-14 versus (R012-20 + R012-14) over M2.5-M14 (all episodes, PPS).
- Incremental efficacy of Fx012-14 versus (R012-20 + R012-14) over D0-M14 (first or only and all episode, ES).
- Vaccine efficacy of Fx012-14 versus Control group over M2.5-M9 (first or only and all episodes, PPS).
- Vaccine efficacy of Fx017-20 versus Control group over M7.5-M14 (first or only and all episodes, PPS)
- Vaccine efficacy of R012-20 + R012-14 versus Control group over M2.5-M9 (first or only and all episodes, PPS).
- Vaccine efficacy of Fx012-14 versus Control group over M2.5-M14 (first or only and all episodes, PPS).
- Vaccine efficacy of Fx017-20 versus Control group over M7.5-M19 (all episodes, PPS).
- Vaccine efficacy of R012-20 + R012-14 versus Control group over M2.5-M14 (first or only and all episodes, PPS).

- Incremental efficacy of Fx017-20 over M7.5-M14 versus Fx012-14 over M2.5-M9 (first or only and all episodes, PPS).
- Incremental efficacy of Fx017-20 over M7.5-M14 versus groups R012-20 + R012-14 over M2.5-M9 (first or only and all episodes, PPS).
- Incremental efficacy of Fx017-20 over M7.5-M19 versus Fx012-14 over M2.5-M14 (first or only and all episodes, PPS).
- Incremental efficacy of Fx017-20 over M7.5-M19 versus groups R012-20 + R012-14 over M2.5-M14 (first or only and all episodes, PPS).
- Vaccine efficacy and impact of R012-20 + R012-14 versus Control group over D0-M14 (first or only for efficacy and all episodes for efficacy and impact, ES).
- Vaccine efficacy and impact of Fx012-14 versus Control group over D0-M14 (first or only for efficacy and all episodes for efficacy and impact, ES).
- Vaccine efficacy and impact of Fx017-20 versus Control group over D0-M14 (first or only and all episodes, ES).
- Vaccine efficacy and impact of R012-20 versus Control group over D0-M20 (all episodes, ES).
- Vaccine efficacy and impact of R012-14 versus Control group over D0-M20 (all episodes, ES).
- Vaccine efficacy and impact of Fx012-14 versus Control group over D0-M20 (all episodes, ES).
- Vaccine efficacy and impact of Fx017-20 versus Control group over D0-M20 (all episodes, ES).

Analysis performed at Month 32:

- Vaccine efficacy and impact of R012-20 versus Control group over D0-M26 (all episodes, ES).
- Vaccine efficacy and impact of R012-14 versus Control group over D0-M26 (all episodes, ES).
- Vaccine efficacy and impact of Fx012-14 versus Control group over D0-M26 (all episodes, ES).
- Vaccine efficacy and impact of Fx017-20 versus Control group over D0-M26 (all episodes, ES).
- Incremental efficacy of Fx017-20 versus R012-20 over M20-M32 (all episodes, PPS).
- Incremental efficacy of Fx012-14 versus R012-14 over M14-M26 (all episodes, PPS).
- Vaccine efficacy and impact of R012-20 versus Control group over D0-M32 (all episodes, ES).

- Vaccine efficacy and impact of R012-14 versus Control group over D0-M32 (all episodes, ES).
- Vaccine efficacy and impact of Fx012-14 versus Control group over D0-M32 (all episodes, ES).
- Vaccine efficacy and impact of Fx017-20 versus Control group over D0-M32 (all episodes, ES).

Analysis performed at Month 50:

- Vaccine efficacy and impact of R012-20 versus Control group over D0-M38 (all episodes, ES).
- Vaccine efficacy and impact of R012-20 versus Control group over D0-M50 (all episodes, ES).
- Vaccine efficacy and impact of R012-14 versus Control group over D0-M38 (all episodes, ES).
- Vaccine efficacy and impact of R012-14 versus Control group over D0-M50 (all episodes, ES).
- Vaccine efficacy and impact of Fx012-14 versus Control group over D0-M38 (all episodes, ES).
- Vaccine efficacy and impact of Fx012-14 versus Control group over D0-M50 (all episodes, ES).
- Vaccine efficacy and impact of Fx017-20 versus Control group over D0-M38 (all episodes, ES).
- Vaccine efficacy and impact of Fx017-20 versus Control group over D0-M50 (all episodes, ES).
- Incremental efficacy of Fx012-14 versus R012-14 over M26-M38 (all episodes, PPS).
- Incremental efficacy of Fx012-14 versus R012-14 over M38-M50 (all episodes, PPS).

B) Incident P. falciparum infections

Analysis performed at Month 20:

- Incremental efficacy of Fx012-14 versus (R012-20 + R012-14) over M2.5-M14 (first or only episode, PPS).
- Incremental efficacy of Fx012-14 versus (R012-20 + R012-14) over D0-M14 (first or only episodes, ES).
- Vaccine efficacy of Fx012-14 versus Control group over M2.5-M9 (first or only episodes, PPS).
- Vaccine efficacy of Fx017-20 versus Control group over M7.5-M14 (first or only episodes, PPS).
- Vaccine efficacy of R012-20 + R012-14 versus Control group over M2.5-M9 (first or only episodes, PPS).
- Vaccine efficacy of Fx012-14 versus Control group over M2.5-M14 (first or only episodes, PPS).
- Vaccine efficacy of Fx017-20 versus Control group over M7.5-M19 (first or only episodes, PPS).
- Vaccine efficacy of R012-20 + R012-14 versus Control group over M2.5-M14 (first or only episodes, PPS).
- Incremental efficacy of Fx017-20 over M7.5-M14 versus Fx012-14 over M2.5-M9 (first or only episodes, PPS).
- Incremental efficacy of Fx017-20 over M7.5-M14 versus groups R012-20 + R012-14) over M2.5-M9 (first or only episodes, PPS).
- Incremental efficacy of Fx017-20 over M7.5-M19 versus Fx012-14 over M2.5-M14 (first or only episodes, PPS).
- Incremental efficacy of Fx017-20 over M7.5-M19 versus groups R012-20 + R012- over M2.5-M14 (first or only episodes, PPS).
- Vaccine efficacy of R012-20 + R012-14 versus Control group over D0-M14 (first or only and all episodes, ES).
- Vaccine efficacy of Fx012-14 versus Control group over D0-M14 (first or only and all episodes, ES).
- Vaccine efficacy of Fx017-20 versus Control group over D0-M14 (first or only and all episodes, ES).
- Vaccine efficacy of R012-20 versus Control group over D0-M20 (all episodes, ES).
- Vaccine efficacy of R012-14 versus Control group over D0-M20 (all episodes, ES).
- Vaccine efficacy of Fx012-14 versus Control group over D0-M20 (all episodes, ES).

204889 (Malaria-094) Statistical Analysis Plan

 Vaccine efficacy of Fx017-20 versus Control group over D0-M20 (all episodes, ES).

C) Prevalent P. falciparum infections

Prevalent *P. falciparum* infections will be assessed in the ES.

Analysis performed at Month 20:

Prevalent P. falciparum infections at each cross-sectional survey

Analysis performed at Month 32:

- Prevalent *P. falciparum* infections at each cross-sectional survey

Analysis performed at Month 50:

- Prevalent *P. falciparum* infections at each cross-sectional survey

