11.7.6. Secondary analyses of efficacy

A) Clinical malaria:

Early follow-up time periods (up to Month 14): Vaccine efficacy against first or only episode as well as all episodes of clinical malaria will be assessed both in the ATP and TVC cohorts.

Longer follow-up time periods (longer than Month 14): Vaccine efficacy against all episodes of clinical malaria will be assessed on the TVC. The analysis of vaccine impact will also be performed on the TVC.

Analysis performed at Month 21:

- Incremental efficacy of Fx012-14-mFxD versus (R012-20 + R012-14-mD) over M2.5-M14 (all episodes, ATP).
- Incremental efficacy of Fx012-14-mFxD versus (R012-20 + R012-14-mD) over D0-M14 (first or only and all episode, TVC).
- Vaccine efficacy of Fx012-14-mFxD versus Control group over M2.5-M9 (first or only and all episodes, ATP).
- Vaccine efficacy of Fx017-mFxD versus Control group over M7.5-M14 (first or only and all episodes, ATP).

- Vaccine efficacy of R012-20 + R012-14-mD versus Control group over M2.5-M9 (first or only and all episodes, ATP).
- Vaccine efficacy of Fx012-14-mFxD versus Control group over M2.5-M14 (first or only and all episodes, ATP).
- Vaccine efficacy of Fx017-mFxD versus Control group over M7.5-M19 (first or only and all episodes, ATP).
- Vaccine efficacy of R012-20 + R012-14-mD versus Control group over M2.5-M14 (first or only and all episodes, ATP).
- Incremental efficacy taking into account incidence in controls: Fx017-mFxD/Control group over M7.5-M14 versus Fx012-14-mFxD/Control group over M2.5-M9 (first or only and all episodes, ATP).
- Incremental efficacy taking into account incidence in controls: Fx017-mFxD/Control group over M7.5-M14 versus groups (R012-20 + R012-14-mD)/Control group over M2.5-M9 (first or only and all episodes, ATP).
- Incremental efficacy taking into account incidence in controls: Fx017-mFxD/Control group over M7.5-M19 versus Fx012-14-mFxD/Control group over M2.5-M14 (first or only and all episodes, ATP).
- Incremental efficacy taking into account incidence in controls: Fx017-mFxD/Control group over M7.5-M19 versus groups R012-20 + R012-14-mD/Control group over M2.5-M14 (first or only and all episodes, ATP).
- Vaccine efficacy of R012-20 + R012-14-mD versus Control group over D0-M14 (first or only and all episodes, TVC).
- Vaccine efficacy of Fx012-14-mFxD versus Control group over D0-M14 (first or only and all episodes, TVC).

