- Vaccine efficacy of Fx017-mFxD versus Control group over D0-M14 (first or only and all episodes, TVC).
- Vaccine efficacy and impact of R012-20 versus Control group over D0-M20 (all episodes, TVC).
- Vaccine efficacy and impact of R012-14-mD versus Control group over D0-M20 (all episodes, TVC).
- Vaccine efficacy and impact of Fx012-14-mFxD versus Control group over D0-M20 (all episodes, TVC).
- Vaccine efficacy and impact of Fx017-mFxD versus Control group over D0-M20 (all episodes, TVC).

Analysis performed at Month 33:

- Vaccine efficacy and impact of R012-20 versus Control group over D0-M26 (all episodes, TVC).
- Vaccine efficacy and impact of R012-14-mD versus Control group over D0-M26 (all episodes, TVC).

- Vaccine efficacy and impact of Fx012-14-mFxD versus Control group over D0-M26 (all episodes, TVC).
- Vaccine efficacy and impact of Fx017-mFxD versus Control group over D0-M26 (all episodes, TVC).
- Incremental efficacy of Fx017-mFxD versus R012-20 over M20-M32 (all episodes, ATP).
- Incremental efficacy of Fx012-14-mFxD versus R012-14-mD over M14-M26 (all episodes, ATP).

Analysis performed at Month 50:

- Vaccine efficacy and impact of R012-20 versus Control group over D0-M38 (all episodes, TVC).
- Vaccine efficacy and impact of R012-20 versus Control group over D0-M50 (all episodes, TVC).
- Vaccine efficacy and impact of R012-14-mD versus Control group over D0-M38 (all episodes, TVC).
- Vaccine efficacy and impact of R012-14-mD versus Control group over D0-M50 (all episodes, TVC).
- Vaccine efficacy and impact of Fx012-14-mFxD versus Control group over D0-M38 (all episodes, TVC).
- Vaccine efficacy and impact of Fx012-14-mFxD versus Control group over D0-M50 (all episodes, TVC).
- Vaccine efficacy and impact of Fx017-mFxD versus Control group over D0-M38 (all episodes, TVC).
- Vaccine efficacy and impact of Fx017-mFxD versus Control group over D0-M50 (all episodes, TVC).
- Incremental efficacy of Fx012-14-mFxD versus R012-14-mD over M26-M38 (all episodes, ATP).
- Incremental efficacy of Fx012-14-mFxD versus R012-14-mD over M38-M50 (all episodes, ATP).

B) Incident *P. falciparum* infections

Early follow-up time periods (up to Month 14): Vaccine efficacy against first or only episode as well as all episodes of incident *P. falciparum* infection will be assessed both in the ATP and TVC cohorts.

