[0-26]	Day of first vaccination of	Date of Month 26/32 visit – 1 or	Fx017-20 vs control Fx012-14 vs control	All episodes	NA
[0-32]	RTS,S or	drop out date		All episodes	
	control	from study	R012-20 vs control	All episodes	
	vaccine	conclusion,	R012-14 vs control	All episodes	
	Vaccino	whichever occurs first	Fx012-14 Vs R012-20 Fx012-14 Vs R012-14	All episodes All episodes	
M50 analys					
[0-38]	Day of first	Date of Month	Fx017-20 vs control	All episodes	NA
	vaccination of	38 visit – 1 or	Fx012-14 vs control	All episodes	
	RTS,S or	drop out date	R012-20 vs control	All episodes	
	control	from study	R012-14 vs control	All episodes	
	vaccine	conclusion,	Fx012-14 Vs R012-20	All episodes	
10.50		whichever occurs first	Fx012-14 Vs R012-14	All episodes	
[0-50]	Day of first	Date of Month	Fx017-20 vs control	All episodes	NA
	vaccination of	50 visit – 1 or	Fx012-14 vs control	All episodes	
	RTS,S or	drop out date	R012-20 vs control	All episodes	
	control vaccine	from study conclusion,	R012-14 vs control	All episodes	
	vaccine	whichever	Fx012-14 Vs R012-20	All episodes	
		occurs first	Fx012-14 Vs R012-14	All episodes	
		Coodio illot	Fx017-20 vs R012-14	All episodes	
			Fx017-20 vs Fx012-14	All episodes	

^{*} if visit date and last contact date are both missing then subjects will be censored at month [x] times 30.5 days post dose 1.

Clinical malaria

For endpoints evaluating the first or only clinical malaria, subjects who withdraw from the study before the study end will contribute to the time at risk computation. This will be explained with the help of the following figure. In these illustrative examples, for the sake of simplicity, it has been considered that visits were effectively conducted at exact monthly intervals.

	M1 30.5d	M2 30.5d	M3 30.5d	M4 30.5d	M5 30.5d	M6 30.5 d	M7 30.5 d	M8 30.5 d	M9 30.5 d	M10 30.5d	-negative +positive
Subject	-	-	-			-	-	+			. missing
Α							—				
Subject	-	-	-	+	-	+	-	-	-	-	
В			—		—				→		

Example: Subject A has two missed visits at month 4 and month 5, and an episode of clinical malaria at start of month 8. This subject will be considered to have an event at month 8, and therefore the time at risk will be (30.5d*7months) 214 days.

For endpoints evaluating all episodes 14 days following each episode will be subtracted from the time at risk (day of episode + 14). For subject B the time at risk will be (30.5*10 months) - (2*14 days) 277 days.

Incident infection

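### Post-booster incremental comparisons are planned only in the per-protocol set, and Fx017-20 is never compared directly with the standard schedule R012-20 in the exposed set

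*SAP*

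**What the plan says.** SAP 7.3.1.6, part A, lists four incremental comparisons for the periods after Doses 4, 5 and 6. One sets the delayed fractional schedule against the standard one: "Incremental efficacy of Fx017-20 versus R012-20 over M20-M32 (all episodes, PPS". The other three set Fx012-14 against R012-14 over M14-M26, M26-M38 and M38-M50, the last being "Incremental efficacy of Fx012-14 versus R012-14 over M38-M50 (all episodes, PPS". All four carry the per-protocol label. SAP 7.3.2.1 says it covers every vaccine efficacy analysis. There, each window that starts at a booster is in Table 4 (per-protocol set), and each window in Table 3 (exposed set) starts at the first vaccination.

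Protocol 11.7.6 gives two instructions, using the older names TVC (exposed set) and ATP (per-protocol set). Its introductory text on clinical malaria says: "Longer follow-up time periods (longer than Month 14): Vaccine efficacy against all episodes of clinical malaria will be assessed on the TVC". The list below that text labels the same four comparisons ATP. For the delayed schedule the entry is "Incremental efficacy of Fx017-mFxD versus R012-20 over M20-M32 (all episodes, ATP"; for yearly dosing the entry after Dose 6 is "Incremental efficacy of Fx012-14-mFxD versus R012-14-mD over M38-M50 (all episodes, ATP", and the entries after Doses 4 and 5 carry the same label. SAP section 10, which records changes from the protocol, does not address the difference.

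**The concern.** The four comparisons serve two secondary objectives: fractional versus full yearly doses, and the Month-7 fractional schedule versus the standard four full doses. Under SAP 6.1.3, a child who misses Dose 4, 5 or 6 is censored at the last contact before the missed dose. Under Table 4, a vaccinated child's risk time starts on the day the booster is received. A child without the booster therefore adds nothing to the window, and membership of the comparison is decided after randomisation.

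That selection may be related to outcome and to group. Under Protocol 7.5, fever or acute disease at the scheduled time defers the dose and may end in withdrawal, so a malaria episode can itself affect whether a child enters a window that counts malaria. The study is also open-label (Protocol 6.3), so return for boosters could differ by schedule.

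For Fx017-20 versus R012-20 there is a further gap. Table 5 compares the delayed schedule with the pooled full-dose groups from 14 days after each group's own Dose 3, in the per-protocol set and on unequal calendar time. No exposed-set row gives a direct contrast with R012-20 since Dose 1.

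**Working it through.** The plan states no figure on this point, so the check is a cross-tabulation followed by an illustrative range.

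**1. Analysis set of the four comparisons (clinical malaria, all episodes)**

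| Comparison | Window | Protocol 11.7.6 list | SAP 7.3.1.6 and Table 4 | Same window in Table 3 |
|---|---|---|---|---|
| Fx012-14 vs R012-14 | M14-M26 | ATP | PPS | none |
| Fx012-14 vs R012-14 | M26-M38 | ATP | PPS | none |
| Fx012-14 vs R012-14 | M38-M50 | ATP | PPS | none |
| Fx017-20 vs R012-20 | M20-M32 | ATP | PPS | none |

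Per-protocol: 4 of 4. Exposed set: 0 of 4.

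**2. Direct comparisons in Table 3.** It has six windows: D0-M14, D0-M20, D0-M26, D0-M32, D0-M38 and D0-M50.

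- Fx017-20 vs Control: 6 of 6.
- Fx017-20 vs R012-20: 0 of 6.
- Fx017-20 vs the pooled full-dose groups: absent at D0-M14, the only window that uses the pooled group.
- Fx017-20 vs another single RTS,S group: D0-M50 only, against R012-14 ("Fx017-20 vs R012-14") and against Fx012-14.
- Fx012-14 vs R012-14, and Fx012-14 vs R012-20: 5 of 6 each (D0-M20 onward).

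Table 6 agrees for the comparisons between RTS,S groups beyond Month 14.

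**3. What a window from Day 0 can show about a booster year.** The 12 months after Dose 4 are 12/26 = 46% of D0-M26. Those after Dose 5 are 12/38 = 32% of D0-M38, and those after Dose 6 are 12/50 = 24% of D0-M50. The rest of each window carries differences that arose earlier, including those from a fractional or full third dose.

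**4. Share of children outside the per-protocol windows.** The documents give no booster uptake. Assume that a constant proportion m of the children still on course misses each dose after the first. The share still on course for a window that follows dose k is (1 - m)^(k-1).

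| m (assumed) | k = 4 (M14-M26, M20-M32) | k = 5 (M26-M38) | k = 6 (M38-M50) |
|---|---|---|---|
| 3% | 0.97^3 = 0.913, 9% outside | 0.97^4 = 0.885, 11% outside | 0.97^5 = 0.859, 14% outside |
| 5% | 0.95^3 = 0.857, 14% outside | 0.95^4 = 0.815, 19% outside | 0.95^5 = 0.774, 23% outside |
| 10% | 0.90^3 = 0.729, 27% outside | 0.90^4 = 0.656, 34% outside | 0.90^5 = 0.590, 41% outside |

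For scale, Protocol 11.4 assumes 250 evaluable children per group of about 300 enrolled. That allows 1 - 250/300 = 17% non-evaluable for the primary analysis, whose window ends before any booster takes effect. It is a planning allowance, not an uptake estimate.

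**5. The two statements in Protocol 11.7.6.** The introductory sentence speaks of vaccine efficacy, so it could be meant only for comparisons with Control. Two things count against that. The parallel sentence on early windows introduces a list that includes incremental comparisons. The list also labels a comparison with Control that runs past Month 14 (Fx017-mFxD, M7.5-M19) as ATP. Neither reading makes the section consistent.

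**The case against.** The case for leaving the plan alone has substance, and it rules out several stronger readings.

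- A reader might infer that the SAP departed from the protocol. It did not: the protocol's own list labels all four comparisons ATP, and the SAP follows it. The conflict lies within Protocol 11.7.6.
- A reader might infer that fractional versus full yearly dosing rests only on children who kept to the schedule. Table 3 plans direct exposed-set comparisons of Fx012-14 with R012-14 over five windows. Only the isolated post-dose periods are missing.
- A reader might infer that malaria during the delay before the Month-7 dose is ignored. Tables 4 and 6 add an M1-M7 comparison of Fx017-20 with Control. It is per-protocol, but it targets that interval.
- A reader might infer that an excess of malaria since Dose 1 under the delayed schedule would stay hidden. Exposed-set comparisons of each schedule with the same Control group on equal calendar time, the cases averted (SAP 7.3.1.4) and the six-month hazard ratios versus Control (SAP 7.3.2.6) would partly reveal it. So would Fx017-20 versus R012-14 over D0-M50.
- A reader might infer that the per-protocol windows hold only children on time for all doses. The out-of-schedule elimination for efficacy in SAP 6.2.2 covers the first three doses only, although the censoring wording in SAP 6.1.3 leaves later timing unclear.

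It is also fair to say that a window defined by a received dose is a legitimate target for a post-dose objective, that the compared groups share booster visits, and that the four comparisons are descriptive under SAP section 8.

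What remains is that reading across two estimates versus Control gives no confidence interval for Fx017-20 versus R012-20, and that no planned post-booster contrast between schedules is free of conditioning on the booster.

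**Conclusion.** The point holds in this limited form. All four post-booster incremental comparisons exist only in the per-protocol set. Fx012-14 versus R012-14 has exposed-set results that accumulate from Day 0 and do not isolate the booster years. Fx017-20 versus the standard schedule R012-20 has no direct exposed-set comparison in any of six windows. The primary analysis is untouched.

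The size of any bias cannot be computed from the documents. The ranges of 9-27% outside M20-M32 and 14-41% outside M38-M50 rest on an assumed 3-10% missing each dose after the first. The larger range applies only to the six-dose window. A share excluded is not itself a bias, and children who miss doses because they leave the study are lost from the exposed set as well.

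**What to change.** 1. Reconcile the introductory text of Protocol 11.7.6 with its list and with SAP 7.3.1.6, stating which set applies to which kind of window, and record the decision in SAP section 10.
2. Add to SAP Table 3, as descriptive rows: Fx017-20 versus R012-20 over D0-M20, D0-M32 and D0-M50 (all episodes), and Fx017-20 versus R012-20 + R012-14 over D0-M14 (the same endpoints as the other rows of that window).
3. Add exposed-set versions of the four post-booster comparisons, with risk time starting at the scheduled Month 14, 20, 26 or 38 visit whether or not the dose was given. Table 4 already starts Control children at the visit. State the start date for a missed visit; the 30.5-day month in the table footnotes could be reused.
4. Group children by assigned schedule in these rows and say so, because SAP 6.1.2 otherwise analyses the exposed set by treatment administered.
5. Keep the per-protocol versions as the on-schedule estimate and report both.

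The same model and data serve. Because SAP section 8 treats these comparisons as descriptive, no alpha is spent. The downside is a modest number of extra rows.
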